5. STUDY DESIGN

This is an open-label study comparing the safety of two treatment cohorts in which radioembolization will be administered using the device SIR-Spheres in combination with regorafenib to patients with mCRC with liver metastases. The two treatment cohorts will be evaluated for safety, ORR, PFS, and OS. Twenty-five patients will be treated in each cohort. The first cohort will complete enrollment before the second cohort opens. There will be no randomization or blinding.

A safety review for toxicity by the Medical Monitor will occur after the first 10 patients have been enrolled in each cohort and treated with one cycle of regorafenib and SIR-spheres (combination therapy) to assess the frequency of \geq Grade 3 adverse events and all SAEs. Accrual will not be halted while the analysis is being conducted.

Stopping Rules Due to Toxicities of Combination Therapy

Stopping rules due to toxicities assessed as related to combination therapy by the Medical Monitor will be defined as follows:

CONFIDENTIAL

STUDY DEVICE: SIR-Spheres®

SCRI INNOVATIONS STUDY NUMBER: GI 189

DATE OF ORIGINAL PROTOCOL: 16 December 2013

Date of Amendment #1: 15 April 2014

Version 2.0

- A patient death considered to be caused by AEs of combination therapy
- A patient with Grade 4 AST, ALT, or irreversible hepatic failure assessed as related to combination therapy;
- More than 2 patients that develop Grade 3 AST, ALT, or total bilirubin assessed as related to combination therapy;
- More than 2 patients develop Grade 3 bleeding in the lung, stomach, small intestine, or liver assessed as related to combination therapy.

If the early stopping rules are met or safety signals emerge from the group of the first 10 patients treated with combination therapy in each cohort, patient recruitment will discontinue and the study will be reassessed. Any outcome of these safety reviews will be communicated in a timely manner to the participating investigators so that they may notify their IRBs.

Blood samples will be collected from all patients prior to the hepatic angiogram and ^{99m}Tc MAA lung shunt scan, on Day 8 after SIR-Spheres treatment, and Day 30 (pre-dose) after SIR-Spheres treatment (see Section 5.1). Expressions of cytokines and proteins will be measured to explore potential biomarkers that may correlate with clinical outcome. The study schema is presented in Figure 1.

CONFIDENTIAL

STUDY DEVICE: SIR-Spheres®

SCRI INNOVATIONS STUDY NUMBER: GI 189

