5.2 Treatment Duration

Patients will be evaluated for toxicity at the start of each 28-day cycle of regorafenib. Patients will be restaged at 6 weeks and 12 weeks after SIR-Spheres in both cohorts, and every 8 weeks thereafter, with imaging, laboratory chemistries, and tumor markers as defined in Appendix A and Appendix B**Error! Reference source not found.** Patients will continue on treatment until progression as defined in Appendix C or intolerance to side effects.

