6.2 Regorafenib Dose Modifications for Non-Hematologic Toxicity

6.2.1 Regorafenib Dose Modifications for Abnormal Liver Function Tests

Regorafenib has been associated with severe drug-induced liver injury with fatal outcome in previous studies. Liver function tests (LFTs) will be monitored during study treatment as described in **Error! Reference source not found.** Appendix A and **Error! Reference source not found.** Appendix B. Dose modifications for regorafenib are recorded in Table 3 below.

Table 3 Regorafenib Dose Modifications for Abnormal Liver Function Tests

Toxicity	Regorafenib Dose
Baseline - Grade 1 And Recurrence OR Baseline Grade 1 – Grade 2 And Recurrence	Treat on time and check AST, ALT and bilirubin 2x/week for 2 weeks followed by weekly assessments for at least 4 weeks.
Baseline - Grade 2	Hold dose until \leq Grade 1 and check AST, ALT and bilirubin 2x/week. Resume regorafenib at 1 lower dose level and check AST, ALT, bilirubin 2x/week for 2 weeks followed by weekly assessments for at least 4 weeks. ^a
Recurrence of Baseline - Grade 2	Discontinue regorafenib ^b .
Baseline Any Grade-Grade 3	Hold dose until \leq Grade 1 for baseline - Grade 1 OR until Grade 2 if baseline was Grade 2.

CONFIDENTIAL

STUDY DEVICE: SIR-Spheres®

SCRI INNOVATIONS STUDY NUMBER: GI 189

DATE OF ORIGINAL PROTOCOL: 16 December 2013

Version 2.0

Date of Amendment #1: 15 April 2014

	Check AST, ALT and bilirubin 2x/week.
	Resume regorafenib at 1 lower dose level and check AST, ALT, bilirubin 2x/week for 2 weeks followed by weekly assessments for at least 4 weeks. ^a
	Note: If ALT or AST >8 x ULN with a concomitant rise in bilirubin (of any degree) compared to previous bilirubin values, consider permanent discontinuation at the first occurrence ^b .
Recurrence of Baseline Any Grade-Grade 3	Discontinue regorafenib ^b .
Baseline Any Grade-Grade 4	Discontinue regorafenib ^b

^a If all values remain stable for 2 full cycles, dose re-escalation may be considered at the discretion of the investigator. After re-escalation AST, ALT, and bilirubin should be checked 2x/week for 2 weeks, followed by weekly assessments for at least 4 weeks.

^b In case of discontinuation, AST, ALT, and bilirubin should be checked 2x/week for 2 weeks, followed by weekly assessments until recovery to baseline.

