7.3.1 Baseline Study Assessments

The following information will be collected and procedures will be performed for each patient at Screening ≤ 21 days prior to initiation of treatment unless otherwise noted:

- Written informed consent prior to any other study-related procedures (≤ 28 days prior to initiation of treatment)
- Medical history

CONFIDENTIAL

STUDY DEVICE: SIR-Spheres®

SCRI INNOVATIONS STUDY NUMBER: GI 189

DATE OF ORIGINAL PROTOCOL: 16 December 2013

Date of Amendment #1: 15 April 2014

Version 2.0

- Physical examination, measurements of height (first visit), weight, and vital signs (resting heart rate, respiratory rate, and oral temperature)
- Blood pressure (BP)
- ECOG PS (Appendix D)
- Concomitant medication review
- CBC (complete blood count) including hemoglobin, hematocrit, white blood cell (WBC) with 3-part differential, and platelets
- CMP to include: glucose, blood urea nitrogen (BUN), creatinine, sodium, potassium, chloride, calcium, carbon dioxide (CO₂), alkaline phosphatase (ALP), AST, ALT, total bilirubin, total protein, and albumin plus lactate dehydrogenase (LDH), and phosphorus.
- PT/PTT/INR
- Serum or urine pregnancy test (must be performed within 72 hours prior to the initiation of treatment)
- Disease assessments:
 - CT scan chest, abdomen, and pelvis (\leq 28 days prior to treatment)
 - CEA tumor marker

7.3.2 Cycle 1, Day 1

If the following are performed within 72 hours of Cycle 1 Day 1 they do not have to be repeated:

- Medical history
- Physical examination, measurements of weight, and vital signs (resting heart rate, respiratory rate, and oral temperature)
- BP
- ECOG PS
- Concomitant medication review
- CBC
- CMP
- PT/PTT/INR
- Serum or urine pregnancy test (must be performed within 72 hours prior to the initiation of treatment)
- CEA tumor marker

CONFIDENTIAL

STUDY DEVICE: SIR-Spheres®

SCRI INNOVATIONS STUDY NUMBER: GI 189

DATE OF ORIGINAL PROTOCOL: 16 December 2013

Date of Amendment #1: 15 April 2014

Version 2.0

7.3.3 Cycle 1, Day 8 and 15

- Physical examination, weight, and vital signs
- BP
- ECOG PS
- AE assessment
- Concomitant medication review
- CBC
- CMP
- PT/PTT/INR (for patients receiving Coumadin therapy)

7.3.4 Cycle 1, Day 22 (assessments to be completed \leq 7 days prior to SIR-Spheres treatment)

- Physical examination, weight, and vital signs
- BP
- ECOG PS
- AE assessment
- Concomitant medication review
- CBC
- CMP
- PT/PTT/INR (for patients receiving Coumadin therapy)

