- Biomarker blood sample collection prior to the hepatic angiogram and 99m Tc MAA lung shunt scan
- CEA tumor marker

The following tests will be obtained 7-4 days prior to SIR-Spheres treatment:

- Hepatic angiogram
- 99m Tc MAA lung shunt scan

7.3.5 Cycle 2, Day 1

SIR-Spheres may not be administered until the patient's hematologic, liver and renal function assessments performed per Section 7.3.4 have been re-confirmed as eligible according to Section 3.1 by the Investigator.

- SIR-Spheres treatment
- BP

CONFIDENTIAL

STUDY DEVICE: SIR-Spheres®

SCRI INNOVATIONS STUDY NUMBER: GI 189

DATE OF ORIGINAL PROTOCOL: 16 December 2013

Date of Amendment #1: 15 April 2014

Version 2.0

7.3.6 Cycle 2, Day 8

- BP
- AE assessment
- CMP
- Biomarker blood sample collection (following SIR-Spheres treatment)

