7.3.7 Cycle 3 and Beyond, Day 1 (± 72 hours)

Regorafenib may not start until the patient's hematologic, liver and renal functions have been reconfirmed as eligible according to the Section 3.1 by the Investigator. Therefore, the regorafenib cycle starts on the day that treatment begins. If liver function toxicities are present, patient may be rechecked weekly for 2 additional weeks. Those patients with persistent liver function toxicities after this time will come off study, but will be followed until resolution.

- Physical examination, weight, and vital signs
- BP
- ECOG PS
- AE assessment
- Concomitant medication review
- CBC
- CMP
- PT/PTT/INR (for patients receiving Coumadin therapy)
- Biomarker blood sample collection (Day 30 (pre-dose) following SIR-Spheres treatment)
- CEA tumor marker

7.3.8 Cycle 3 and Beyond, Day 15

- PT/PTT/INR (for patients receiving Coumadin therapy)

7.4 Study Treatment Assessments – COHORT 2

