7.4.4 Cycle 2, Day 1 (± 72 hours)

Regorafenib may not start until the patient's hematologic, liver and renal functions have been re-confirmed as eligible according to Section 3.1 by the Investigator. Therefore, the regorafenib cycle starts on the day that treatment begins. If liver function toxicities are present, patient may be rechecked weekly for 2 additional weeks. Those patients with persistent liver function toxicities after this time will come off study, but will be followed until resolution.

CONFIDENTIAL

STUDY DEVICE: SIR-Spheres®

SCRI INNOVATIONS STUDY NUMBER: GI 189

DATE OF ORIGINAL PROTOCOL: 16 December 2013

Date of Amendment #1: 15 April 2014

Version 2.0

- Physical examination, weight, and vital signs
- BP
- ECOG PS
- AE assessment
- Concomitant medication review
- CBC
- CMP
- PT/PTT/INR (for patients receiving Coumadin therapy)
- CEA tumor marker
- Biomarker blood sample collection (Day 30 following SIR-Spheres treatment only)

7.4.5 Cycle 2, Day 8 and 15

- Physical examination, weight, and vital signs
- BP
- ECOG PS
- AE assessment
- Concomitant medication review
- CBC
- CMP
- PT/PTT/INR (for patients receiving Coumadin therapy)

7.4.6 Cycle 2, Day 22

- BP

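### Cohort 1's first regorafenib cycle after SIR-Spheres has liver tests, blood counts and AE checks scheduled on Day 1 only; Cohort 2's matching cycle has them on Days 1, 8 and 15

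*Protocol*

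**What the plan says.** **Cohort 1.** SIR-Spheres is given in Cycle 2, so Cycle 3 is the first regorafenib cycle afterwards. The Protocol does not schedule Cycle 3 separately from later cycles.

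- Under "7.3.7 Cycle 3 and Beyond, Day 1", CMP, CBC and AE assessment are listed once, on Day 1.
- The text has no Day 8 visit for that cycle.
- Under "7.3.8 Cycle 3 and Beyond, Day 15", the only entry is PT/PTT/INR, for patients on Coumadin.
- The weekly on-drug tests are at "7.3.3 Cycle 1, Day 8 and 15", before SIR-Spheres. After SIR-Spheres there is a CMP at "7.3.6 Cycle 2, Day 8", before the restart.

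**Cohort 2.** SIR-Spheres is Cycle 1 and the first regorafenib cycle is Cycle 2. It has its own schedule: CMP, CBC and AE assessment on Day 1 (7.4.4) and again at "7.4.5 Cycle 2, Day 8 and 15".

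**General statements.** Section 5.2 says: "Patients will be evaluated for toxicity at the start of each 28-day cycle of regorafenib". Section 6.2.1 warns: "Regorafenib has been associated with severe drug-induced liver injury with fatal outcome in previous studies". Section 5 opens: "This is an open-label study comparing the safety of two treatment cohorts".

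The CMP rows of Appendices A and B agree with this as far as their columns can be read: one mark in Cohort 1's Cycle 3 column group, and marks on Days 1, 8 and 15 of Cohort 2's Cycle 2. The columns are partly displaced in the copy reviewed, so the point rests on the Section 7 text.

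**The concern.** In both cohorts the closer testing follows a patient's first exposure to regorafenib. In Cohort 2 that is also the first exposure after liver irradiation. In Cohort 1 it is not, because the closely tested cycle is over before SIR-Spheres is given. The first cycle in which Cohort 1 patients take regorafenib on an irradiated liver therefore has no scheduled liver test after Day 1.

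Two things are at stake. One is patient safety: a 21-day dosing block of a drug with known fatal liver injury, shortly after radioembolization, without a routine check. The other is the comparison that a reader will want from a study of sequence, namely liver toxicity once both treatments have been given. A transient laboratory abnormality is recorded only if blood is drawn, and in this period blood is drawn more often in Cohort 2.

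**Working it through.** The plan gives no figure to reproduce. The check sets the two schedules on one time axis.

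**Inputs**
- Day 0 is SIR-Spheres. Day 8 of the SIR-Spheres cycle is therefore day 7 (7.3.6, 7.4.3).
- Regorafenib starts or restarts 2 to 4 weeks later (Section 10.1), and cycles last 28 days.
- CMP is on Day 1 only in Cohort 1's Cycle 3, and on Days 1, 8 and 15 in Cohort 2's Cycle 2.

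**Step 1: scheduled CMP days after SIR-Spheres, up to Day 1 of the next cycle**

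| Rest before regorafenib | Cohort 1 | Cohort 2 | Tests between restart Day 1 and next Day 1 |
|---|---|---|---|
| 14 days | 7, 14, 42 | 7, 14, 21, 28, 42 | 0 v 2 |
| 21 days | 7, 21, 49 | 7, 21, 28, 35, 49 | 0 v 2 |
| 28 days | 7, 28, 56 | 7, 28, 35, 42, 56 | 0 v 2 |

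The longest gap within the cycle is 28 days in Cohort 1 and 14 days in Cohort 2. Optional weekly rechecks for liver toxicity are left out; they come before the restart and do not change the last column.

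**Step 2: mean delay to the next scheduled test.** Assume a lasting elevation with onset uniform over the 28-day cycle, and scheduled tests only. With test intervals of length g, the mean delay is Σg² / (2 × 28).
- Cohort 1: 28² / 56 = 14.0 days.
- Cohort 2: (7² + 7² + 14²) / 56 = 294 / 56 = 5.25 days.

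The whole difference comes from onset in the first 14 days of the cycle. There the mean delay is 28 − 7 = 21 days in Cohort 1 and 7 / 2 = 3.5 days in Cohort 2. For onset in the last 14 days both cohorts wait for the same test, with a mean of 14 / 2 = 7 days. Averaging the halves gives (21 + 7) / 2 = 14.0 and (3.5 + 7) / 2 = 5.25.

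**Step 3: do other provisions fill the gap?**
- Rechecks under 7.3.7 apply before the restart, and only if liver toxicity is present.
- Table 3 calls for twice-weekly tests, starting at a new Grade 1 rise, but a test must first show that rise.
- Section 5.2 mentions laboratory chemistries at Week 6 restaging and refers to the appendices for them; Section 7.5 lists only imaging. Week 6 is day 42. For an on-time restart that is already Day 1 of the next cycle, so nothing is added. After a 28-day rest, labs drawn then would fall on Cohort 1's Cycle 3 Day 15 and make the count 1 v 2. After a 21-day rest they would add one test in each cohort, 1 v 3.

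**Step 4: the whole treatment period.** Now count from first study treatment as day 0, with an on-time restart and post-treatment CMPs through day 70.
- Cohort 1: days 7, 14, 21, 35, 42, 70. Total 6.
- Cohort 2: days 7, 14, 21, 28, 42, 70. Total 6.

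The totals are equal. Three of Cohort 1's six tests (days 7, 14, 21) come before SIR-Spheres, which is why the imbalance appears only after it.

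**The case against.** The strongest defence is that the schedule has a logic. Each cohort is tested weekly on first meeting regorafenib, and Cohort 1 enters Cycle 3 with that experience and any dose reductions behind it. Restart also requires liver function to be reconfirmed against the eligibility limits, and a new Grade 1 rise on day 7 or at restart brings in Table 3's intensive testing. The 28-day gap therefore applies only to patients with no new elevation at those tests. Section 8.2 defers to labelling and institutional practice, which may add tests that the documents do not show. All of this stands and narrows the point, but none of it schedules a test inside the cycle for a patient who looked well at restart. Cycle 1 tests cannot detect toxicity of a combination that has not yet been given.

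It is also fair that the missing tests would do little for radioembolization-induced liver disease. Section 8.1.3 places it about 4 to 8 weeks after treatment. With an on-time restart, Cohort 2's extra tests on days 21 and 28 come before that window or at its start, and later onsets meet the same day 42 test in both cohorts.

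Two stronger readings are tempting. A reader might infer that the AE summary by maximum grade (Section 10.4.4) is tilted against Cohort 2. The documents do not support that as a consequence of this schedule alone: treatment-emergent events count from first study treatment, and over that period the scheduled tests are 6 v 6. Neither document plans a table limited to the period after SIR-Spheres.

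A reader might also infer that the Grade 3 liver stopping rule is less likely to be met in Cohort 1, by a calculable amount. Any such probability needs an event rate that the documents do not give, uniform onset, and no Table 3 testing. Moreover, Sections 5 and 10.4.3 time the review to ten patients treated with one regorafenib cycle and SIR-Spheres. In Cohort 1 that can be read as complete before Cycle 3 begins. No figure for the stopping rule can be defended.

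**Conclusion.** The concern holds as a monitoring gap confined to the combination period. On the Section 7 text, Cohort 1's first regorafenib cycle after SIR-Spheres has no scheduled CMP, CBC or AE assessment between its Day 1 and the next Day 1, against two of each in Cohort 2. For an on-time restart with no new elevation, that means no scheduled liver test between days 14 and 42. The count of 0 v 2 needs no distributional assumption, though Week 6 labs would raise Cohort 1's count to one after a longer rest. The mean delays of 14.0 and 5.25 days assume a lasting elevation, uniform onset and scheduled tests only; symptom-driven tests would reduce the difference.

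The consequences are weaker protection of Cohort 1 patients in that cycle, and unequal ascertainment in any comparison of liver toxicity after SIR-Spheres. The study is non-randomized with no formal testing, so this does not undermine a planned inference. It is worth correcting because the safety of the combination is what the trial exists to assess and the correction is cheap.

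**What to change.** Add a Cohort 1 visit section for Cycle 3, Days 8 and 15, with at least AE assessment, CBC and CMP, using the content of 7.4.5 as the model. Mark those days as applying to Cycle 3 only in Appendix A. Cohort 1's CMP days after SIR-Spheres then match Cohort 2's (7, 14, 21, 28, 42 for an on-time restart), and the longest gap in the cycle falls from 28 to 14 days. The cost is at most 2 × 25 = 50 short laboratory visits, fewer if some patients stop before Cycle 3, and no extra patients.

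The SAP is dated 22 May 2018, well after the April 2014 amendment, and the planned study duration is 16 months, so Cohort 1 may already have been treated; the documents do not say. In that case add one SAP table of worst AST, ALT and bilirubin grade by cohort, limited to the scheduled visits both cohorts share after SIR-Spheres: Day 8, restart Day 1, and Day 1 of the next cycle. The SAP's table list contains no laboratory table at present. This would put the comparison on equal testing, but it cannot recover elevations that were never measured, and its footnote should say so.

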7.4.1 Baseline Study Assessments

The following information will be collected and procedures will be performed for each patient at Screening ≤ 21 days prior to initiation of treatment unless otherwise noted. The following must be repeated or performed ≤ 7 days of Cycle 1 Day 1 to document Cycle 1 Day 1 assessments prior to SIR-Spheres treatment unless otherwise noted:

CONFIDENTIAL

STUDY DEVICE: SIR-Spheres®

SCRI INNOVATIONS STUDY NUMBER: GI 189

DATE OF ORIGINAL PROTOCOL: 16 December 2013

Date of Amendment #1: 15 April 2014

Version 2.0

- Written informed consent prior to any other study-related procedures (≤ 28 days prior to initiation of treatment)
- Medical history
- Physical examination, measurements of height (first visit), weight, and vital signs (resting heart rate, respiratory rate, and oral temperature)
- Blood pressure (BP)
- ECOG PS (Appendix D)
- Concomitant medication review
- CBC (complete blood count) including hemoglobin, hematocrit, white blood cell (WBC) with 3-part differential, and platelets
- CMP to include: glucose, blood urea nitrogen (BUN), creatinine, sodium, potassium, chloride, calcium, carbon dioxide (CO₂), alkaline phosphatase (ALP), AST, ALT, total bilirubin, total protein, and albumin plus lactate dehydrogenase (LDH), and phosphorus.
- PT/PTT/INR
- Serum or urine pregnancy test (must be performed within 72 hours prior to the initiation of treatment)
- Biomarker blood sample collection prior to the hepatic angiogram and ^{99m}Tc MAA lung shunt scan, which will be obtained 7-4 days prior to SIR-Spheres treatment
- Disease assessments:
 - CT scan chest, abdomen, and pelvis (≤ 28 days prior to treatment)
 - CEA tumor marker

7.4.2 Cycle 1, Day 1

- SIR-Spheres treatment

7.4.3 Cycle 1, Day 8

- AE assessment
- CMP
- Biomarker blood sample collection (following SIR-Spheres treatment)

7.4.4 Cycle 2, Day 1 (± 72 hours)

Regorafenib may not start until the patient's hematologic, liver and renal functions have been re-confirmed as eligible according to Section 3.1 by the Investigator. Therefore, the regorafenib cycle starts on the day that treatment begins. If liver function toxicities are present, patient may be rechecked weekly for 2 additional weeks. Those patients with persistent liver function toxicities after this time will come off study, but will be followed until resolution.

CONFIDENTIAL

STUDY DEVICE: SIR-Spheres®

SCRI INNOVATIONS STUDY NUMBER: GI 189

DATE OF ORIGINAL PROTOCOL: 16 December 2013

Date of Amendment #1: 15 April 2014

Version 2.0

- Physical examination, weight, and vital signs
- BP
- ECOG PS
- AE assessment
- Concomitant medication review
- CBC
- CMP
- PT/PTT/INR (for patients receiving Coumadin therapy)
- CEA tumor marker
- Biomarker blood sample collection (Day 30 following SIR-Spheres treatment only)

7.4.5 Cycle 2, Day 8 and 15

- Physical examination, weight, and vital signs
- BP
- ECOG PS
- AE assessment
- Concomitant medication review
- CBC
- CMP
- PT/PTT/INR (for patients receiving Coumadin therapy)

7.4.6 Cycle 2, Day 22

- BP

7.4.7 Cycle 3 and Beyond, Day 1 (± 72 hours)

- Physical examination, weight, and vital signs
- BP
- ECOG PS
- AE assessment
- Concomitant medication review
- CBC

CONFIDENTIAL

STUDY DEVICE: SIR-Spheres®

SCRI INNOVATIONS STUDY NUMBER: GI 189

DATE OF ORIGINAL PROTOCOL: 16 December 2013

Date of Amendment #1: 15 April 2014

Version 2.0

- CMP
- PT/PTT/INR (for patients receiving Coumadin therapy)
- CEA tumor marker

7.4.8 Cycle 3, Day 8

- BP

7.4.9 Cycle 3 and Beyond, Day 15

- PT/PTT/INR (for patients receiving Coumadin therapy)

7.5 Response Assessment Week 6 and Week 12 after SIR-Spheres, and then every 8 Weeks

Patients will be reassessed for response according to RECIST v1.1 (Appendix C) at Weeks 6 and 12 after SIR-Spheres with CT scans in both cohorts. After completing SIR-Spheres and 2 cycles of regorafenib patients may continue regorafenib treatment alone, if tumor response is stable or better. Patients continuing treatment after Week 12 will have response re-assessed at 8-week intervals (± 1 week). Patients with progressive disease (PD) or unacceptable toxicity will be discontinued from the study.

The following assessment will be performed:

- CT scan of chest, abdomen, and pelvis. If CT chest is normal at baseline this does not have to be repeated with each restaging unless there is a clinical reason to do so. If a CT scan is not possible, then an MRI may be used.

As noted above in the Day 1 assessments for all cycles, CEA tumor markers must be assessed on Day 1 of each cycle and at the End-of-Treatment visit.

